## **9.2 Efficacy Assessments**

The following efficacy assessments will be performed by appropriately trained staff/clinical examiners, at the times and in the order defined in the [Study Procedures](#) section of this protocol.

### **9.2.1 Subject Questionnaires**

On assessment days, the subject will complete 3 questionnaires that assess the subject's gum health and OHRQoL and at Visit 3 subjects randomized to the denture adhesive groups will also complete a questionnaire to evaluate the sensory attributes of the adhesive. The subject responses should be transcribed by the study staff to the CRF. The study staff should be mindful that whilst the questionnaires do not solicit safety information, any information on safety outcomes recorded by subjects on a questionnaire should be evaluated by the investigator to ensure all AEs are recorded. To ensure that the examiner who performs the MSA and OST assessments is blinded to the assignment of denture adhesive treatment, the examiner will not have access to these questionnaires and should not have knowledge of who is completing the questionnaires and will remain blinded to the distribution and completion of all questionnaires.

Questionnaires should be completed one at a time, and the next questionnaire should not be administered to the subject until they have returned the previous completed questionnaire. For consistency purposes, it is intended that the order that subjects receive their questionnaires remains regular for the duration of the study. The gum-comfort questionnaire is the first to be administered since this is the primary endpoint for this study. The OHIP-Edent will then be administered and then the subject will have the MSA/OST assessments performed. Finally the

GOHAI questionnaire should be administered. This ordering has been chosen to allow the subject some respite from questionnaires with the OST/MSA between the OHIP-Edent and GOHAI questionnaires.

Subjects should be advised in the correct completion of the questionnaires at every visit and should ambiguous response be given (i.e. more than one result circled for a question) be clarified with the subject before they leave the study site.

### 9.2.1.1 Gum-Comfort Questionnaire

The gum-comfort questionnaire will be administered to the subjects prior to their OST examination and administration of the OHIP-Edent questionnaire at the baseline and all assessment visits (Visits 1-5). This questionnaire is comprised of 5 questions that inform on the subject-perceived comfort of their denture-bearing tissues. The questions have 5 possible responses (Agree Strongly, Agree Somewhat, Neither Agree or Disagree, Disagree Somewhat, Disagree Strongly) and are scored on a 0 (Agree Strongly) to 4 (Disagree Strongly) scale for all questions. Thus, the range of the total questionnaire score is 0-20 where a low score is more favorable.

### 9.2.1.2 OHIP-Edent Questionnaire

The OHIP-Edent questionnaire is a well-established questionnaire for evaluation of OHRqoL ([Allen and Locker, 2002](#)). This questionnaire will be administered to subjects after completion of the gum comfort questionnaire and prior to their OST examination at the baseline and all assessment visits (Visits 1-5). This questionnaire is comprised of 19 questions grouped into 6 functional domains per Table 9-1. The questions have 5 possible responses (Never, Rarely, Occasionally, Often and Very Often) that the subjects should indicate by marking the appropriate box. The responses are scored on a 0 (Never) to 4 (Very Often) scale for all questions and thus a low score is more favorable and the overall score range is 0-76 where 0 is the best possible score.

**Table 9-1 The functional domains of the OHIP-Edent questionnaire.**

Domain	Questions	Score range
Functional limitations	1-3	0-12
Physical pain	4-7	0-16
Psychological discomfort	8-9	0-8
Physical disability	10-12	0-12
Psychological disability	13-14	0-8
Social disability	15-19	0-20

### 9.2.1.3 GOHAI Questionnaire

The GOHAI questionnaire ([Atchison and Dolan, 1990a](#)) will be administered to the subjects at all assessment visits after the gum-comfort questionnaire has been completed. This questionnaire is comprised of 12 questions with 6 possible responses to each question (always, very often, often, sometimes, seldom and never). The responses are scored on a 0 (always) -5 (never) scale for all questions except 3, 5 and 7 where the scoring is reversed, and thus the range of scores for the questionnaire is 0-60, where 60 is the best possible score. The questions are grouped into 3 domains as in Table 9-2.

**Table 9-2 The functional domains of the GOHAI questionnaire**

Domain	Questions	Score range	Meaning
Functional	1-4	0-20	Subject's ability to eat, speak and swallow
Psychosocial	6,7,9-11	0-25	Subject's concerns, relationships and appearance
Pain/Discomfort	5,8,12	0-15	Subject's discomfort during chewing, sensitivity to hot/cold/sweets and use of medications to manage oral pain.

#### 9.2.1.4 Sensory Questionnaire

The sensory questionnaire will be completed by subjects after the GOHAI questionnaire has been completed and retrieved at Visit 3 only. This questionnaire comprises 6 questions that inform on the sensory attributes of the adhesive, and thus will only be administered to subjects randomized to the adhesive group. The questionnaire allows for 5 possible responses (Agree Strongly, Agree Somewhat, Neither Agree or Disagree, Disagree Somewhat, Disagree Strongly) and are scored on a 0 (Agree Strongly) to 4 (Disagree Strongly) scale for all questions. Thus the range of the questionnaire score is 0-24 where a low score is more favorable.

#### 9.2.2 Mucosal Score Assessment (MSA)

The health of the denture-bearing tissues should be assessed using the scale described by Henriksen et al ([Henriksen et al, 1999](#)) and summarized in Table 9-3.

The MSA should be performed by a suitably qualified dental professional and ideally the same examiner should be used throughout the study. The MSA will be made on the denture bearing tissues for either/both of the subject's dentures across the whole mouth and therefore the examiner should record the highest applicable score (ie should a subject have normal appearance of their mandibula denture-bearing tissue, yet display ulcers caused by denture in the maxillary tissue, a score of 3 should apply). The result of the examination will be recorded in the CRF.

The MSA may be performed at the same time as the OST examination. The absence of any residual denture adhesive in the mouth must be confirmed by a second (non-blinded) examiner prior to the subject attending to the MSA or OST examination to ensure the OST/MSA assessor remains blinded to treatment.

**Table 9-3 The MSA Scale per Henriksen ([Henriksen et al, 1999](#))**

Score	Appearance
1	Normal appearance of the gingiva and oral mucosa
2	Mild inflammation 
 
• slight redness and/or hypertrophy/hyperplasia of the gingiva
 
• slight redness in some areas of the palatal mucosa, including red spots indicating inflamed salivary duct orifices
 

3	Moderate inflammation 
 
• marked redness and hypertrophy/hyperplasia of the gingiva, which bleeds easily when pressure is applied
 
• marked redness in large areas (2/3 or more) of the palate
 
• marked inflammatory redness of the oral mucosa in sites other than in the palate
 
• ulceration(s) caused by denture(s)
 
• red and inflamed fibro-epithelial hyperplasias caused by denture(s)
 

4	Severe inflammation 
 
• severe redness and hypertro hypertrophy/hyperplasia of the gingiva
 
• spontaneous gingival bleeding
 

Score	Appearance
	
 
marked palatal granulations
 
inflamed oral mucosal areas which easily “break” and bleed under pressure, e.g., when dentures are inserted
 

### 9.3 Safety and Other Assessments

The following safety assessments will be performed by appropriately trained staff/clinical examiners, at the times and in the order defined in the [Study Procedures](#) section of this protocol.

#### 9.3.1 Oral Soft Tissue (OST) Examination - Edentulous

The OST examination should be performed by a suitably qualified dental professional and ideally the same examiner should be used throughout the study. The OST Exam-Edentulous will include the labial mucosa (including lips), buccal mucosa, tongue, edentulous gingival mucosa, sublingual area, hard and soft palates, mucogingival folds, submandibular area, salivary glands, tonsillar and pharyngeal areas. Observations will be made of any erythema, desquamation and ulcerations, and other relevant clinical observations. The results of the examination will be recorded in the CRF as either normal or abnormal. The location and brief description of any abnormalities will also be recorded.

An OST examination should be performed at screening and at each visit to the study site and the findings recorded in the CRF. A single examiner should complete this assessment for all the subjects. If this is not possible, then the same examiner should perform this procedure for the same subject for all the visits wherever possible.

The OST examination may be performed at the same time as the MSA. The absence of any residual denture adhesive in the mouth must be confirmed by a second (non-blinded) examiner prior to the subject attending to the MSA or OST examination to ensure the OST/MSA assessor remains blinded to treatment.

#### 9.3.2 Pregnancy Testing

For female subjects of childbearing potential, a urine pregnancy test, will be performed at every visit to the study site. Results will be obtained prior to dosing during each period.

The investigator and site personnel will remind subjects at each visit to inform site personnel if their menstrual cycle has changed or if they have any other reason to suspect they may be pregnant (e.g. had unprotected intercourse since the last visit).

A negative pregnancy result is required before the subject may receive the investigational product. Pregnancy tests will also be done whenever one menstrual cycle is missed during the active study period (or when potential pregnancy is otherwise suspected). Pregnancy tests may also be repeated as per request of IRBs/ECs or if required by local regulations.

In the case of a positive confirmed pregnancy, the subject will be withdrawn from administration of investigational product and from the study.

## 10 ADVERSE EVENT AND SERIOUS ADVERSE EVENTS

### 10.1 Definition of an Adverse Event (AE)

An AE is any untoward medical occurrence in a clinical study subject, temporally associated with the use of a study product including any washout or lead-in product (or medical device),

whether or not considered related to the study product, including any washout or lead-in product (or medical device).

NOTE: An AE can therefore be any unfavorable and unintended sign (including an abnormal laboratory finding), symptom, or disease (new or exacerbated) temporally associated with the use of a study product including any washout or lead-in product (or medical device).

**Events Meeting the AE Definition:**

- Any abnormal laboratory test results (hematology, clinical chemistry, or urinalysis) or other safety assessments (e.g. ECG, radiological scans, vital sign measurements), including those that worsen from baseline, considered clinically significant in the medical and scientific judgment of the investigator (i.e., not related to progression of underlying disease).
- Exacerbation of a chronic or intermittent pre-existing condition including either an increase in frequency and/or intensity of the condition.
- New conditions detected or diagnosed after study product administration even though it may have been present before the start of the study.
- Signs, symptoms, or the clinical sequelae of a suspected drug-drug interaction.
- Signs, symptoms, or the clinical sequelae of a suspected overdose of either study product or a concomitant medication. Overdose per se will not be reported as an AE/SAE unless it is an intentional overdose taken with possible suicidal/self-harming intent. Such overdoses should be reported regardless of sequelae.
- "Lack of efficacy" or "failure of expected pharmacological action" per se will not be reported as an AE. Such instances will be captured in the efficacy assessments. However, the signs, symptoms, and/or clinical sequelae resulting from lack of efficacy will be reported as AE if they fulfill the definition of an AE.

**Events NOT meeting the AE definition:**

- Any clinically significant abnormal laboratory findings (if applicable) or other abnormal safety assessments which are associated with the underlying disease, unless judged by the investigator to be more severe than expected for the subject's condition.
- The disease/disorder being studied or expected progression, signs, or symptoms of the disease/disorder being studied, unless more severe than expected for the subject's condition.
- Medical or surgical procedure (e.g. endoscopy, appendectomy) is not the AE. The condition that leads to the procedure is an AE (e.g. appendicitis).
- Situations where an untoward medical occurrence did not occur (social and/or convenience admission to a hospital).
- Anticipated day-to-day fluctuations of pre-existing disease(s) or condition(s) present or detected at the start of the study that do not worsen.

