## 4.2 Rationale for Study Design

The duration of this study will be 12 weeks. In a previous study (Nicolas et al, 2010) the OHRQoL was assessed after 12 and 24 weeks use of an adhesive and whilst in general large improvements were observed over the 24 weeks, the greatest improvement was observed between baseline and 12 weeks, with more modest improvement observed thereafter. To minimise subject exposure a 12-week period is therefore deemed sufficient.

Subjects who already adopt a cleaning routine will be recruited (outlined in Inclusion/ Exclusion Criteria) as the cleanliness of the denture may impact the efficacy of the adhesive. All subjects enrolled to this study will continue to use their existing denture cleaning methodologies through the duration of the study.

Subjects in this study must be habitual wearers of a full denture in either or both arches to ensure that they are familiar with their dentures in place and are likely to continue wearing them during waking hours. Subjects who are xerostomic are excluded since the proper function of denture adhesives requires adequate hydration from saliva.

Demographic information will be recorded as part of this study, including age, race and gender. In accordance with US FDA guidelines (US FDA, 2005) the ethnicity of subjects will also be captured.

Dentures are unique to each individual. Therefore, the most efficient approach to evaluating their performance with different adhesives or 'no adhesive' is a within subject comparison (i.e.

a crossover design), however such a design is not practicable in a long-term study: a parallel design is therefore appropriate. The study design does not allow for double blinding since the subjects themselves will know whether they are using adhesive or not. The study examiner who performs the MSA and OST examination will be blinded to the treatments. The study is therefore described as single-blind (safety assessor and the examiner determining the MSA score).

An OST examination will be conducted at each treatment to evaluate potential AEs.

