15. A subject with OST examination findings such as stomatitis, open sores, lesions, or swelling which in the opinion of the investigator, would interfere with the conduct of the study. Mild, chronic conditions commonly expected from the use of dentures in the investigators opinion, are acceptable in this study.
16. A subject who is using any medication that, in the opinion of the investigator, would interfere with the conduct of the study.

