4.6.2 Other Safety Variables

Medical Device Incidents

Medical devices are being provided by GSK CH for use in this study; the medical devices in this study are the test denture adhesive, the denture brush, and the denture cleansing paste.

A medical device incident is any malfunction or deterioration in the characteristics and/or performance of a device as well as any inadequacy in the labeling or the instructions for use which, directly or indirectly, might lead to or might have led to the death of a subject/user/other person or to a serious deterioration in his/her state of health.

All Incidents will be listed in Listing [16.2.7.2](#).

Oral Soft Tissue Examination

Summary of oral soft tissue (OST) examination results (frequency counts and percentages) will be tabulated in [Table 14.3.1](#) at each visit and listed in [Listing 16.2.9.1](#).

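### Section 10.1 gives two overlapping rules for a new or worse denture-bearing lesion, and the planned by-visit OST table cannot show how many findings are new

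*Protocol*

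**What the plan says.** Protocol section 10.1 holds two lists.

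- **Events that are AEs.** These include "New conditions detected or diagnosed after study product administration even though it may have been present before the start of the study" and "Exacerbation of a chronic or intermittent pre-existing condition including either an increase in frequency and/or intensity of the condition". The first bullet of this list also takes in abnormal safety assessments, including ones worse than at baseline, when the investigator finds them clinically significant.
- **Events that are not AEs.** These include "The disease/disorder being studied or expected progression, signs, or symptoms of the disease/disorder being studied, unless more severe than expected" and "other abnormal safety assessments which are associated with the underlying disease, unless judged by the investigator to be more severe than expected". In both clauses the benchmark is what would be expected for that subject.

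The disorder under study is not named. Section 10.2 adds that something that is not an AE cannot be a serious AE.

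On the examination itself, section 4.2 gives its purpose: "An OST examination will be conducted at each treatment to evaluate potential AEs". Section 9.3.1 says "The results of the examination will be recorded in the CRF as either normal or abnormal", and the location and a short description of each abnormality are kept as well. Exclusion criterion 15 in section 5.3 lets some abnormality in at entry: "Mild, chronic conditions commonly expected from the use of dentures in the investigators opinion, are acceptable in this study". For the analysis, SAP 4.6.2 says "Summary of oral soft tissue (OST) examination results (frequency counts and percentages) will be tabulated" for each visit, with a listing. Protocol section 12.2.7 says no more than that OST results are tabulated.

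**The concern.** The product sits against the mucosa, and treatment-emergent AEs are the only safety endpoint. A new or worse sore under the denture is therefore the finding on which the safety report most needs a clear rule. Two things stand in the way.

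First, the same lesion can be read as an AE under one list and as not an AE under the other, and nothing says which list governs. The choice falls to a person whose blinding the documents leave open.

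Second, the examination meant to inform that choice is summarised without reference to each subject's own baseline, in a population that may start with abnormalities. A lesion judged to be expected could then be absent from the AE tables and also not visible in the OST summary.

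**Working it through.** The plan gives no figure on this point, so there is none to reproduce. The check is a side-by-side reading followed by a count illustration.

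**1. Does one lesion fit both lists?** The documents enrol healthy subjects and name no disorder. A secondary objective, however, is to reduce irritation of the denture-bearing mucosa, and grade 3 of the MSA (protocol Table 9-3) includes ulceration from dentures. If that irritation is taken as the disorder under study:

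| Finding | AE list | Non-AE list |
|---|---|---|
| New denture ulcer, subject normal at entry | AE (new condition) | Not an AE if judged no more severe than expected for this subject |
| Mild redness at entry, now more marked | AE (exacerbation) | Not an AE if judged no more severe than expected for this subject |
| Mild redness at entry, unchanged | Not listed | Not an AE |

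The lists agree on the third row only. The first two turn on the undefined disorder and on what is expected.

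**2. Who decides, and is that person blinded?** Protocol section 10.4 gives AE reporting to the investigator or a medically qualified designee.

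- *Pointing to blinding:* the safety assessor is described as blinded (4.1, 4.2), dispensing staff are kept out of safety assessment (6.1.2, 6.5), and the investigator decides whether to break the blind (6.6).
- *Pointing the other way:* section 6.5 refers to the investigator knowing the allocation, and section 8.3 has the investigator or a designee review the diary, which records product use. Section 9.2.1 sends safety information from questionnaires to the investigator, and only the adhesive arm completes the sensory questionnaire.

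The status is unclear. The documents establish neither blinding nor its absence.

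**3. What can a by-visit count show?** Let *N* be the subjects examined in an arm, *b* the number abnormal at baseline, *r* the number who resolve and *x* the number newly abnormal.

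- By-visit table: (b − r + x) / N
- Shift table, normal to abnormal: x / (N − b)

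N = 63 is the planned arm size (protocol section 1). The values of b, r and x are assumptions, with r = x and no dropout.

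| b | By-visit result, any r = x | New, x = 0 | New, x = 5 | New, x = 10 |
|---|---|---|---|---|
| 10 | 10/63 = 15.9% | 0/53 = 0% | 5/53 = 9.4% | 10/53 = 18.9% |
| 20 | 20/63 = 31.7% | 0/43 = 0% | 5/43 = 11.6% | 10/43 = 23.3% |
| 30 | 30/63 = 47.6% | 0/33 = 0% | 5/33 = 15.2% | 10/33 = 30.3% |

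Within each row the by-visit figure never moves. Two arms at b = 20, one with no change and one with 10 resolved and 10 new, would both print 20/63.

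**4. What does a normal/abnormal shift table still miss?** A subject abnormal at baseline who gains a second lesion elsewhere stays in the abnormal-to-abnormal cell. Finding that subject needs a comparison of the recorded locations and descriptions, which is why the fix has two parts.

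**The case against.** The other side is strong on several points, and much of it stands.

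- **A reader might infer that section 10.1 simply removes mucosal lesions from AE reporting.** It does not. The exclusion is conditional, and the yardstick is the subject's own condition. The general definition and the first list both point towards recording what is new or worse. What remains is an overlap with an unnamed disorder.
- **A reader might infer that nothing links the OST to AEs.** The first list covers clinically significant abnormal safety assessments that worsen from baseline, and section 10.4 requires directly observed AEs to be reported. A link exists. It leads back to the same judgement, because that bullet also sets aside progression of underlying disease.
- **A reader might infer that staff who know the arm decide what counts as an AE.** The evidence in step 2 is mixed, so this is not established. Nor do the documents support any figure for unequal AE recording between arms, and none is offered here.
- **A reader might infer that new lesions go unrecorded.** The OST is done at Visit 1 and every later visit, location and description are kept, and results are listed by subject. New findings can be traced. The gap is mainly in the summary, although no severity grade is recorded, so worsening at the same site would show only in the description.
- **The MSA is a blinded check with change from baseline.** SAP 4.5.1.3 compares it between arms at each week. It helps, but it is an efficacy measure, is confined to denture-bearing tissue and keeps only the worst score. A further lesion at an unchanged grade does not register, and sites such as the tongue and lips are outside it.

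Finally, the SAP's list of data displays survives only as a file name. A shift table there cannot be ruled out, but the SAP text plans none.

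**Conclusion.** The point holds as a minor one. Section 10.1 leaves an unresolved overlap for new or worsened denture-bearing lesions, and the blinding of the person who resolves it is not stated. The planned OST summary gives net prevalence only. With 20 of 63 abnormal at baseline it cannot tell 0/43 from 10/43 newly abnormal (0% against 23.3%). With 10 or 30 abnormal at baseline, the same 10 new findings are 18.9% or 30.3% of those at risk.

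This rests on three assumptions: that denture-bearing irritation could be taken as the disorder under study, that a real share of subjects enter with an abnormal OST, and that some findings resolve while others appear. The documents allow all three but quantify none. Sample size, power and the primary analysis are untouched.

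**What to change.** **SAP 4.6.2.** Add an OST baseline-by-visit shift table by product group (normal to abnormal and abnormal to normal). Add a count of subjects with any abnormality that is new relative to their own baseline, taken from the recorded location and description. If feasible, add one CRF field per abnormality (unchanged, worse or new), completed by the blinded examiner.

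**Protocol section 10.1.** Name the disorder to which the exclusion refers, or say that there is none. Reconcile the two lists for OST findings so that new or worsened ones are handled alike in both arms. Making every new abnormality an AE, whatever its clinical significance, is debatable and is not needed for this point.

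**Protocol sections 6.5 and 10.4.** State who makes the AE decision and whether that person is blinded.

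**Cost.** One extra table from data already collected, a few sentences, possibly one CRF field, and possibly a few more minor oral AEs reported.
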